Subjects will be assessed for response by computed tomography (CT) or Magnetic Resonance Imaging (MRI). All measurable and non-measurable lesions must be documented at screening (within 28 days prior to randomization) and re-assessed at each subsequent tumor evaluation (every 8 weeks (+/- 1 week) for the first year, every 12 weeks (+/- 1 week) while the patient is on study). Tumor assessments with CT or MRI scans of the brain, chest, abdomen, and pelvis will be performed until disease progression after the second combo treatment per RECIST v1.1.

For patients who discontinue study treatment for reason other than investigator-determined disease progression, tumor assessments should continue to be performed as scheduled.

Patients will continue to be on study and can be switched to the subsequent therapy after PD as per protocol in both arm A and B.

In case of an interruption of the treatment in arm C, reason other than investigator-determined disease progression, during the first 8 weeks (2 cycles of therapy), patient can continue the study treatment with combo immuno, as scheduled.

For patients with palpable/superficial lesions, clinical disease assessments by physical examination should be performed at baseline and throughout study treatment as clinically indicated. Color photographs with ruler/calipers will be taken at baseline and at all subsequent tumor assessment time points.

The National Cancer Institute Common Toxicity Criteria for Adverse Events (NCI CTC-AE) Version 4.03 will be used to evaluate the clinical safety of the treatment in this study. Patients will be assessed for AEs at each clinical visit and as necessary throughout the study.

Biomarker study

A correlative biological study will be performed for the evaluation of biomarkers on the biological sample available (paraffin-embedded tissue, frozen tissue, blood, serum, etc.). Approximately 80-90 patients will take part in the biomarker study.

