20.2.1. SECONDARY EFFICACY VARIABLES & DERIVATIONS

The secondary efficacy endpoints are:

- a) Total PFS, calculated from the date of randomization until the date of the second progression (i.e., the progression to second treatment); any progression or death will be considered as an event if patient cannot complete treatment sequence.
 Any patient not known to have experienced progression or died at the time of data analysis will be censored at the time of the last recorded date on which the patient was known to be alive without disease progression.
 Total PFS (months) = [(Date of second progression or any progression/death or last contact – date of randomization +1)/30.4]
- b) 3 years PFS rate (PFSR), calculated from the date of randomization until the date of progression or death from any cause. This rate estimates the proportion of patients who did not progress and were alive 3 years after randomization.
- c) Percentage of patients alive at 2 and 3 years;
- d) Best overall response rate (BORR), defined as the best response designation, as determined by the investigator, recorded between the date of randomization and the date of objectively documented progression per RECIST version 1.1 criteria;
- e) Duration of response (DoR), calculated as the time from the date of first documented response (CR or PR) until the date of the first documented progression or death due to

¹ where 0=censored; 1 = event.

underlying cancer. If a patient with a CR or PR has no progression or death due to underlying cancer, the patient is censored at the date of last adequate tumor assessment;

DoR (months) = $[(\text{Date of first documented progression/death due to underlying cancer or date of last tumor assessment} - \text{date of first CR or PR} + 1)/30.4]$

- f) Health-related quality of life (HRQoL), by means of the 30-item European Organisation for Research and Treatment of Cancer quality of life questionnaire (EORTC QLQ-C30);
- g) General health status, by means of the European Quality of Life 5-Dimensions (EQ-5D) questionnaire;
- h) Impairment of work productivity and activity, by means of the Work Productivity and Activity Impairment: General Health (WPAI:GH) questionnaire.

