20.2.2. ANALYSIS OF SECONDARY EFFICACY VARIABLES

The secondary efficacy analyses will be performed in ITT set.

The following statistical methods will be applied on the secondary efficacy endpoints:

- a) Total PFS: The estimates of the survivor function using the Kaplan-Meier approach will be displayed graphically by treatment arm. Median time and the corresponding two-sided 95% confidence interval will be presented together with the estimates for the other quartiles (SAS procedure PROC LIFETEST) by treatment arm separately.
 A Cox's proportional hazard regression model will also be performed to assess the influence of some baseline covariates on total PFS. Covariates of interest are those reported in [Paragraph 9.1](#). Hazard ratios estimates with their 95% confidence limits will be also presented (SAS procedure PROC PHREG).
- b) 3-years PFSR: The PFSR at 3 years will be estimated by the Kaplan-Meier method. The 95% confidence intervals for the PFSR will be estimated using Greenwood's estimate of the standard error (SE) and a linear transformation of the progression-free survival function.
- c) Percentage of patients alive at 2 and 3 years will be reported using Wilson score intervals for each treatment arm.
- d) BORR: Default summary statistics of the best overall response from the date of randomization to the date of objectively documented progression per RECIST version 1.1 criteria will be presented, by treatment arm.
 For each treatment arm, the Overall Response Rate (ORR) will be calculated as the percentage of patients in the ITT set who have a CR or PR before any evidence of progression (as defined by RECIST).
 A 95% confidence interval (CI) will be derived for the ORR using Wilson score intervals (CIs for a single proportion).
- e) The estimates of the survivor function of DoR using the Kaplan-Meier approach will be displayed graphically by treatment arm. Median time and the corresponding two-sided 95% confidence interval will be presented together with the estimates for the other quartiles (SAS procedure PROC LIFETEST) by treatment arm separately.
 A Cox's proportional hazard regression model will also be performed to assess the influence of some baseline covariates on DoR. Covariates of interest are those reported in [Paragraph 9.1](#). Hazard ratios estimates with their 95% confidence limits will be also presented (SAS procedure PROC PHREG).

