	Censored	n (%)	xx (xx.x)	xx (xx.x)	xx (xx.x)

Notes:

Duration of Response (DoR) is defined as the time from the date of first documented response (CR or PR) to the date of first documented progression or death due to underlying cancer;

DoR (months) = [(Date of first documented progression/death due to underlying cancer or date of last tumor assessment - date of first CR or PR +1)]/30.4.

If a patient with a CR or PR has no progression or death due to underlying cancer, the patient is censored at the date of last adequate tumor assessment.

Percentages are calculated relative to the total number of the patients in the ITT set by treatment arm.

DoR (months) will be estimated using Kaplan-Meier method.

Source: XXXX.SAS, Run on DDMMYYYY

TABLE 34. Analysis of Secondary Endpoint: Summary of Duration of Response (DoR) (cont.)

POPULATION: ITT

Arm A

[figure not shown]
Time Interval (months)	Censoring Indicator	Survival Distribution Function Estimate	Survival Standard Failure	Survival Standard Error	Number Failed	Number Left	SDF Lower 95% Confidence Limit	SDF Upper 95% Confidence Limit
x.xxxx	x	x.xxxx	x	x	x	xx	x.xxxx	x.xxxx
x.xxxx	x	x.xxxx	x	x	x	xx	x.xxxx	x.xxxx
x.xxxx	x	x.xxxx	x	x	x	xx	x.xxxx	x.xxxx
x.xxxx	x	x.xxxx	x	x	x	xx	x.xxxx	x.xxxx
x.xxxx	x	x.xxxx	x	x	x	xx	x.xxxx	x.xxxx
x.xxxx	x	x.xxxx	x	x	x	xx	x.xxxx	x.xxxx
x.xxxx	x	x.xxxx	x	x	x	xx	x.xxxx	x.xxxx
x.xxxx	x	x.xxxx	x	x	x	xx	x.xxxx	x.xxxx
x.xxxx	x	x.xxxx	x	x	x	xx	x.xxxx	x.xxxx

Source: XXXX.SAS, Run on DDMMYYYY

< Note for SAS Programmer: This must be produced for each arm separately >

TABLE 34. Analysis of Secondary Endpoint: Summary of Duration of Response (DoR) (cont.)

POPULATION: ITT

Source: XXXX.SAS, Run on DDMMYYYY

TABLE 35. Analysis of Secondary Endpoint: Predictive factors of Duration of Response

POPULATION: ITT

The PHREG Procedure

Model Information

Data Set	xxxx	
Dependent Variable	xxxx	Duration of Response (Months)
Censoring Variable	xxxx	Censor
Censoring Value(s)	0	
Ties Handling	BRESLOW	

Number of Observations Read	xxx
Number of Observations Used	xxx

Summary of the Number of Event and Censored Values

Total	Event	Censored	Percent Censored
xxx	xx	xx	xx.xx

Convergence Status

Convergence criterion (GCONV=1E-8) satisfied.

Model Fit Statistics

Criterion	Without Covariates	With Covariates
-2 LOG L	xxxx.xxx	xxxx.xxx
AIC	xxxx.xxx	xxxx.xxx
SBC	xxxx.xxx	xxxx.xxx

Testing Global Null Hypothesis: BETA=0

Test	Chi-Square	DF	Pr > ChiSq
Likelihood Ratio	xx.xxxx	xx	x.xxxx

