XXX	XXX	XXXXXXXX	DDMMYYYY	DDMMYYYY	X	XXX	XXX	XXX
XXX	XXX	XXXXXXXX	DDMMYYYY	DDMMYYYY	X	XXX	XXX	XXX

Source: XXXX.SAS, Run on DDMMYYYY

Listing 52) Total progression free survival, 3-years PFS and BORR

POPULATION: ITT

Treatment Arm	Site	Patient Number	Date of randomization (DDMMYYYY)	Date of second progression / last contact date (DDMMYYYY)	Censoring (0=censored, 1=event)	Total PFS (months)	3-years PFS (Yes/No)	BORR
XXX	XXX	XXXXXXXX X	DDMMYYYY	DDMMYYYY	X	XXX	XXX	XXX
XXX	XXX	XXXXXXXX X	DDMMYYYY	DDMMYYYY	X	XXX	XXX	XXX
XXX	XXX	XXXXXXXX X	DDMMYYYY	DDMMYYYY	X	XXX	XXX	XXX
XXX	XXX	XXXXXXXX X	DDMMYYYY	DDMMYYYY	X	XXX	XXX	XXX
XXX	XXX	XXXXXXXX X	DDMMYYYY	DDMMYYYY	X	XXX	XXX	XXX
XXX	XXX	XXXXXXXX X	DDMMYYYY	DDMMYYYY	X	XXX	XXX	XXX
XXX	XXX	XXXXXXXX X	DDMMYYYY	DDMMYYYY	X	XXX	XXX	XXX
XXX	XXX	XXXXXXXX X	DDMMYYYY	DDMMYYYY	X	XXX	XXX	XXX

Source: XXXX.SAS, Run on DDMMYYYY

Listing 53) Duration of Response (DoR)

POPULATION: ITT

Treatment Arm	Site	Patient Number	Date of first documented response (CR or PR) (DDMMYYYY)	Date of first progression or death du to cancer / last tumor assessment date (DDMMYYYY)	Censoring (0=censored, 1=event)	DoR (months)
XXX	XXX	XXXXXXXX	DDMMYYYY	DDMMYYYY	X	XXX
XXX	XXX	XXXXXXXX	DDMMYYYY	DDMMYYYY	X	XXX
XXX	XXX	XXXXXXXX	DDMMYYYY	DDMMYYYY	X	XXX
XXX	XXX	XXXXXXXX	DDMMYYYY	DDMMYYYY	X	XXX
XXX	XXX	XXXXXXXX	DDMMYYYY	DDMMYYYY	X	XXX
XXX	XXX	XXXXXXXX	DDMMYYYY	DDMMYYYY	X	XXX
XXX	XXX	XXXXXXXX	DDMMYYYY	DDMMYYYY	X	XXX

Source: XXXX.SAS, Run on DDMMYYYY

Listing 54) Adverse events

POPULATION: SAF

Patient Number	AE#	Date on which the investigator finds out of the event (DDMMYYYY)	Description of event	Preferred Term	SOC	Start Date (DDMMYYYY) / End Date (DDMMYYYY)	Causality	Ongoing?	Related to	SAE	AESI	Grade	Outcome	Action taken	Trt. Req.?
XXXXX	X	DDMONYYYY	XXXXXX	XXXXXXXXXX	XXXXXXXXXX	DDMONYYYY / DDMONYYYY	XXXXXX	XXXXXX	XXXXXX	X	X	xxx	xxx	xxx	xxx
	X	DDMONYYYY	XXXXXX	XXXXXXXXXX	XXXXXXXXXX	DDMONYYYY / DDMONYYYY	XXXXXX	XXXXXX	XXXXXX	X	X	xxx	xxx	xxx	xxx
	X	DDMONYYYY	XXXXXX	XXXXXXXXXX	XXXXXXXXXX	DDMONYYYY / DDMONYYYY	XXXXXX	XXXXXX	XXXXXX	X	X	xxx	xxx	xxx	xxx
	X	DDMONYYYY	XXXXXX	XXXXXXXXXX	XXXXXXXXXX	DDMONYYYY / DDMONYYYY	XXXXXX	XXXXXX	XXXXXX	X	X	xxx	xxx	xxx	xxx
XXXX	X	DDMONYYYY	XXXXXX	XXXXXXXXXX	XXXXXXXXXX	DDMONYYYY / DDMONYYYY	XXXXXX	XXXXXX	XXXXXX	X	X	xxx	xxx	xxx	xxx
	X	DDMONYYYY	XXXXXX	XXXXXXXXXX	XXXXXXXXXX	DDMONYYYY / DDMONYYYY	XXXXXX	XXXXXX	XXXXXX	X	X	xxx	xxx	xxx	xxx

Source: XXXX.SAS, Run on DDMMYYYY

Listing 55) Adverse events related to Ipilimumab

POPULATION: SAF

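### Duration of response lacks the pre-progression limit that the response rate carries, so a first response after the switch gives a negative or inconsistent duration; its table also uses the wrong denominator

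*Supplement*

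**What the plan says.** - **Response rate.** SAP 20.2.2(d) defines ORR as the "percentage of patients in the ITT set who have a CR or PR before any evidence of progression". Best overall response in 20.2.1(d) has the same window: the best designation "recorded between the date of randomization and the date of objectively documented progression per RECIST version 1.1 criteria".
- **Duration of response.** SAP 20.2.1(e) has DoR "calculated as the time from the date of first documented response (CR or PR) until the date of the first documented progression", or death from the cancer. A responder with neither is censored at the last adequate tumour assessment. The formula is (end date - date of first CR or PR + 1)/30.4. It sets no limit on when the response may occur.
- **Outputs.** The Table 34 note repeats the definition and formula. The end-date column of Listing 53 is headed "Date of first progression or death du to cancer / last tumor assessment date", with no link to the response or to a treatment line. (Tables are cited by their shell numbers. The list of tables in section 26 numbers the two DoR tables 32 and 33; the shells number them 34 and 35.)
- **Follow-up.** Under SAP 4.4, patients in Arms A and B can move to the next therapy after progression, and CT or MRI assessments "will be performed until disease progression after the second combo treatment per RECIST v1.1". Under SAP 4.3, Arm C also changes at progression, from Combo Immuno back to Combo Target.
- **Table 34 percentages.** The note reads: "Percentages are calculated relative to the total number of the patients in the ITT set by treatment arm".

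**The concern.** ORR and DoR should describe the same responders, and as written they need not. In a design with two treatment lines and up to two progressions, a patient may progress on one combination without having responded and then reach a first CR or PR on the next. ORR excludes that patient. The DoR text does not, and it ends the interval at a progression that came before the response.

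DoR feeds Kaplan-Meier medians by arm and a Cox model with treatment sequence as a covariate (SAP 9.1 and 20.2.2(e)). The SAP has no rule for a negative time. Whether such patients are dropped, counted as events or given a later end date would be left to the programmer.

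**Working it through.** The SAP states no figure for ORR or DoR, so there is none to reproduce. The check applies the SAP's formula to illustrative dates.

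**Inputs.** The formula and the 30.4-day month come from 20.2.1(e). The scan interval of 8 weeks in year one and 12 weeks after that comes from 4.4. The dates are assumed: first progression at week 8 (day 56), first CR or PR at week 16 (day 112) on the next combination, second progression at week 40 (day 280).

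**One patient, three readings.**

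| Reading | Calculation | DoR |
|---|---|---|
| End date is the first progression overall | (56 - 112 + 1)/30.4 = -55/30.4 | -1.81 months |
| End date is the first progression after the response | (280 - 112 + 1)/30.4 = 169/30.4 | +5.56 months, for an ORR non-responder |
| DoR limited to ORR responders | patient not included | none |

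**Control case.** A patient who responds at week 8 and first progresses at week 40 has (280 - 56 + 1)/30.4 = 225/30.4 = 7.40 months under every reading. Only patients whose first response follows a progression are affected.

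**Size of the literal value.** With a gap of g days from first progression to first response, DoR = (1 - g)/30.4. It is zero at g = 1 and negative for any longer gap:

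| Gap (days) | DoR (months) |
|---|---|
| 49 | -1.58 |
| 56 | -1.81 |
| 63 | -2.04 |
| 84 | -2.73 |
| 112 | -3.65 |
| 168 | -5.49 |

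**Is the literal reading plausible?** Item (a) of the same section, on total PFS, says explicitly when it means the second progression. Item (e) says first. A programmer following the text and the Listing 53 heading could reasonably take the first progression on record.

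**Table 34 denominator.** Only patients with a CR or PR can be an event or censored for DoR. With R responders among N ITT patients, the two percentages add to 100 x R/N. For an assumed 45 responders among the planned 69 in an arm, that is 45/69 = 65%, not 100%. The same note suits OS and total PFS, where every ITT patient is one or the other.

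**The case against.** The strongest defence is that duration of response presupposes a response followed by its loss. Item (e) also comes directly after item (d), whose window closes at progression, so a sensible analyst would carry that window over. This has weight: the SAP is silent on the DoR window and does not declare that a response at any time counts. A reader might infer that late responders will certainly receive negative durations. The text does not support that, because the negative value needs both dates to be read literally. What remains is that the text, formula, table note and listing all omit the limit, and nothing in the SAP selects a reading.

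The SAP rests on protocol version 10.0, which is not among the documents here and may settle how response is judged after a switch. That could narrow the problem. It would not mend a derivation that the SAP states in full without the limit.

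A bad value would also be visible. Listing 53 prints both dates and the derived duration, and the Table 35 shell prints the observations read and used. That helps detection but does not say what to do.

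A reader might also infer that Arms A and B are affected and Arm C hardly at all, since Arm C's planned 8-week change is not triggered by progression. But Arm C later switches at progression too, and the SAP gives nothing from which to calculate a contrast.

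On Table 34, the denominator is disclosed and the counts let a reader recover the responder total. No Kaplan-Meier estimate changes. The percentages are still uninformative as event and censoring proportions.

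**Conclusion.** The point holds as a gap in specification. The DoR population and end date are not tied to the ORR responder definition, and in this sequencing design the literal rule misfires for any patient whose first CR or PR comes more than one day after the first progression. The -1.81 and +5.56 month values show the conflict on assumed dates; they are not estimates of bias. The Table 34 denominator is wrong for DoR on any reading.

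The number of patients affected cannot be computed from the SAP. A reader might try to derive one from the 65% in SAP 4.2. With 69 patients per arm, 60% to 100% of non-responders switching and 20% to 65% of those responding, this gives 69 x 0.35 x 0.6 x 0.2 = 2.9 to 69 x 0.35 x 1.0 x 0.65 = 15.7 patients. The documents do not support that range. The 65% is an aggregate clinical activity rate for ipilimumab/nivolumab, used there only to obtain a median PFS. It is not a response rate, and it does not describe the targeted combination that opens Arm A. The switching and second-line response rates have no source in the SAP.

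DoR is secondary, the decision rule uses survival at 24 months, and no between-arm tests are planned (SAP 8.3). The gap should be closed before analysis, but it does not touch the primary conclusion.

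**What to change.** 1. In 20.2.1(e), the notes to Tables 34 and 35, and Listing 53, state that DoR is derived only for patients counted as responders in ORR. It runs from the first CR or PR recorded before any progression to the first subsequent progression or death from the underlying cancer. With this restriction the first progression necessarily follows the response, so the two end-date readings coincide and no negative value can arise.
2. In Table 34, change the denominator of the event and censored percentages from all ITT patients to responders in the arm.
3. If response to the second combination is to be reported, present it as a separate descriptive DoR, from that response to the next progression or cancer death.

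The cost is a sentence in the SAP, the matching table notes and a listing heading. No new data are needed, and patients who respond before progression keep the same values.

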20. EFFICACY OUTCOMES

20.1. PRIMARY EFFICACY

20.1.1. PRIMARY EFFICACY VARIABLE & DERIVATION

OS is the primary endpoint of the study. OS will be calculated from the date of randomization until the date of death from any cause. Any patient not known to have died at the time of data analysis will be censored at the time of the last recorded date on which the patient was known to be alive.

OS (months) = $[(\text{Date of death or last contact} - \text{date of randomization} + 1) / 30.4]$

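### Duration of response censors deaths not due to the underlying cancer, so its Kaplan-Meier curve and median overstate how long responders stay alive and in response

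*Supplement*

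**What the plan says.** Item (e) of SAP section 20.2.1 runs DoR from the first CR or PR "until the date of the first documented progression or death due to" the underlying cancer. The censoring rule follows: "If a patient with a CR or PR has no progression or death due to underlying cancer, the patient is censored" at the last adequate tumor assessment. The derivation formula in the same item uses the same two end dates.

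The shells repeat the definition, so it is not a slip of wording. The Table 34 note takes DoR "to the date of first documented progression or death due to underlying cancer", and the Listing 53 column header reads "Date of first progression or death du to cancer / last tumor assessment date".

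The neighbouring endpoints treat death differently:
- **OS (20.1.1):** "OS will be calculated from the date of randomization until the date of death from any cause".
- **3-year PFS rate (20.2.1 b):** "calculated from the date of randomization until the date of progression or death from any cause".
- **Total PFS (20.2.1 a):** a death is an event when it prevents the patient from completing the sequence.

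Section 20.2.2(e) analyses DoR by Kaplan-Meier in each arm, with medians and other quartiles. It adds a Cox model whose covariates (section 9.1) include the assigned sequence. The SAP contains no competing-risk analysis of DoR and no any-cause sensitivity analysis.

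**The concern.** Kaplan-Meier assumes that a censored patient could still have the event later, at the same rate as those still followed. That is reasonable for a responder who is alive at data cut-off. It is not reasonable for one who has died, because that response cannot continue. The curve then describes a hypothetical setting in which nobody dies of other causes, yet the output is labelled simply as duration of response.

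A fatal drug reaction in a responder shows the effect. The same death is an event for OS and for the PFS rate but a censored observation for DoR. A reader who sets the DoR median beside the PFS rate would be comparing quantities defined on different events, and the outputs would not say so.

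At stake is how the DoR curves, quartiles and arm-level hazard ratios are read in a trial whose stated aim is to find the best sequence.

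**Working it through.** **The plan's own figures.** The documents give no planning figure for DoR. The sample size in section 4.2 rests on 24-month survival. With 69 patients, at least 30 alive, and 33% against 48%, the exact one-sided alpha is 0.0446 and the power 0.808; 207/0.9 = 230. These reproduce, and a change to DoR does not touch them.

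**Inputs for DoR.** The event and censoring rules come from 20.2.1(e) and the Kaplan-Meier method from 20.2.2(e). The share q of DoR-ending events that are non-cancer deaths is not in the documents; it is assumed and varied from 2% to 20%. The 15-month median below is also an assumption, chosen only to put numbers in.

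**Formula.** Let λ be the hazard of progression or cancer death and μ the hazard of other death, both constant.
- The plan's rule estimates exp(-λt), with median ln2/λ.
- The any-cause definition gives exp(-(λ+μ)t), with median ln2/(λ+μ).
- Since q = μ/(λ+μ), we have λ = (1-q)(λ+μ), so the ratio of the two medians is (λ+μ)/λ = 1/(1-q).

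**Results when the plan's rule reports a median of 15 months** (any-cause median = 15 × (1-q)):

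| q | Inflation 1/(1-q) | Any-cause median (months) | 24-month rate, plan's rule | 24-month rate, any cause |
|---|---|---|---|---|
| 2% | 1.02 | 14.7 | 33.0% | 32.2% |
| 5% | 1.05 | 14.25 | 33.0% | 31.1% |
| 10% | 1.11 | 13.5 | 33.0% | 29.2% |
| 20% | 1.25 | 12.0 | 33.0% | 25.0% |

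**Check on censoring at the last scan.** The plan censors at the last scan, which is slightly before the death. A simulation of 200,000 responders used scans every 8 weeks, then every 12, and assumed follow-up of 24 to 60 months. The plan's rule gave medians of 14.92, 14.98 and 14.80 months at q = 5%, 10% and 20%, against any-cause medians of 14.24, 13.57 and 11.98. The ratios are 1.05, 1.10 and 1.23, close to the formula.

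**Arms.** Suppose two arms have the same any-cause DoR hazard but shares q1 and q2. The cancer-only hazard ratio of the second to the first is then (1-q2)/(1-q1). For 0% against 5% it is 0.95, for 0% against 10% it is 0.90, and for equal shares it is 1.00. Under section 4.3 the drugs given before first progression are Combo Target in A, Combo Immuno in B, and 8 weeks of Combo Target followed by Combo Immuno in C. Equal shares are therefore not assured, but no rate of non-cancer death is given for any arm.

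**The case against.** The strongest reply is that the SAP defines a cancer-specific DoR and applies it consistently, so the bias exists only relative to a different estimand. That is partly right: the choice is one of estimand. It does not rescue the Kaplan-Meier curve and median, which are not the probability or time of remaining alive and in response when other deaths compete. Nor does the SAP label them as cancer-specific.

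The reply also limits what can be claimed. Four stronger readings are tempting, and the documents do not support them:
- **The more toxic sequence is flattered.** A reader might infer this from the different drugs. Without non-cancer death rates by arm, unequal inflation is only a possibility.
- **Arm C responders are exposed to both regimens.** Combo Target in C stops at 8 weeks, about when the first scheduled scan falls (section 4.4). Treatment while in documented response is then mainly Combo Immuno, as in B.
- **The Cox model is wrong.** Censoring competing deaths gives a valid cause-specific hazard ratio for progression or cancer death. It needs that label; it is not an error.
- **Individual responses are recorded as longer.** The patient is censored at a scan before death. It is the arm's estimate that rises.

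The consequence is also limited. DoR is secondary, section 8.3 plans no comparative tests, and the decision rule uses 24-month survival. Deaths remain visible in OS, the PFS rate and the fatal adverse event tables, although those tables are not linked to responders. A rule for attributing cause of death may sit in the protocol, which was not among the documents reviewed, so its absence from the SAP is not counted here.

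**Conclusion.** The point holds for the DoR curve, median and other quartiles. Relative to time alive and in response they are biased upward, and they do not match the all-cause definition used for OS and the PFS rate. The direction follows from the definition. The size depends on the unknown share q: negligible at 2%, modest at 5% to 10%, and 25% on the median at 20%, all under constant hazards. Whether the inflation differs between arms, and which arm would gain, cannot be settled from the documents. The change should be made because it is simple and removes a known distortion; it does not affect the primary endpoint or the sample size.

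**What to change.** Define DoR as the time from first CR or PR to first documented progression or death from any cause. Censor only responders who are alive and progression-free, at their last adequate tumor assessment. Amend section 20.2.1(e), its formula, the Table 34 note and the Listing 53 header.

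Section 4.6 states that nothing changes from the protocol's planned analysis. If the protocol carries the cancer-only definition, record the departure there.

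The cancer-death-only version may be kept as a labelled sensitivity analysis. If it stays as the main definition instead, label the Cox result as a cause-specific hazard ratio.

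The cost is one definition, its formula and two shell edits, plus the section 4.6 entry if it is needed. Dates of death from any cause are already needed for OS (Listing 51), so no new data are required. The downside is that reported DoR may be slightly shorter.
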